1 INTRODUCTION

1.1 STUDY OBJECTIVES

1.1.1 Primary Objectives:

- To evaluate the feasibility of molecular testing in adrenal neoplasm FNA biopsy samples.
- To determine the accuracy of novel diagnostic molecular markers in clinical adrenal FNA biopsy and surgically resected samples.

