Postoperative histopathologic examination to distinguish between malignant and benign primary adrenal tumors is also difficult and problematic. For adrenocortical neoplasms, the Weiss histologic criterion is most commonly used, but is imprecise [21-23]. This means even patients with histologically diagnosed adrenocortical adenoma require continued follow-up because some will develop metastatic disease [11].

In summary, although adrenocortical carcinomas tend to be larger than benign tumors, tumor size, even when combined with imaging features, is not accurate enough to use for making management decisions for most tumors that are less than 6 cm. Furthermore, imaging studies such as MRI and CT scans underestimate adrenal tumor size by 16% to 47%, and are less accurate in smaller tumors [24-26]. Therefore, there is a significant need for biomarkers that can distinguish benign from malignant adrenal tumors for determining the need for adrenalectomy, for selecting the appropriate surgical approach, and for determining the appropriate follow up.

We and others have used genome profiling approaches (mRNA, microRNA) to identify diagnostic and prognostic markers of malignant adrenocortical tumors [27-31]. In our studies, we have identified several novel diagnostic markers with excellent accuracy for distinguishing between benign and primary malignant adrenocortical tumors ([Appendix A](#)). While these markers could be used in post-surgical resection samples in equivocal cases, the most helpful clinical application of these markers would be preoperatively in clinical fine needle aspiration biopsy samples. Therefore, we propose to test the feasibility and accuracy of using this panel of markers in fine needle aspiration samples of patients with adrenal neoplasm with the exception of pheochromocytoma that are greater than 2 cm. For cytologic examination, fine needle aspiration biopsy has a 67%-100% adequacy rate [32, 33]. Our previous studies in thyroid fine needle aspiration biopsy samples indicate an adequate yield of nucleic acid for multigene expression analysis [34]. Moreover, we are able to determine gene expression levels in as little as 10 adrenocortical carcinoma cells by quantitative RT PCR ([Appendix B](#)).

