8 STATISTICAL CONSIDERATIONS

The primary objective of this study is to determine the ability of a set of markers to distinguish between benign and malignant adrenocortical neoplasms.

Patients with adrenal neoplasms greater than 2 cm will be enrolled onto the trial and a set of novel diagnostic and prognostic molecular markers will be evaluated. It is anticipated that approximately 10% of patients enrolled will have a malignant mass and 90% will be benign. Based upon pilot data, it is expected that the classification accuracy of the proposed methods will be 90% or better, but this study is intended to determine if this is correct and to improve the precision of the estimate of these results.

Assuming that 10% of patients have a malignant mass, it would be desirable to estimate the fraction of these correctly identified as being malignant, with a confidence interval width of +/-10% or less. Enrolling thirty five (35) patients who are ultimately determined to have malignant masses would permit an associated two-sided 95% confidence interval around 90% to have a width of +/-9.9%. It would also be desirable to estimate the fraction correctly identified as being benign. Enrolling 200 patients who are ultimately determined to have benign masses would permit an associated two-sided 95% confidence interval around 90% to have a width of +/-4.2%. Greater numbers of patients and a higher probability of correct classification will result in greater precision of the estimated classification probability.

Because the estimate is likely to be much less precise for identifying the malignant cases than for identifying those that are benign, it is important to enroll sufficient patients to ensure that at least 35 malignant cases are evaluated. Thus, if 10% is a reasonable estimate of the proportion of all patients expected to have malignant masses, it would be

desirable to enroll 350-500 total patients in order to have a reasonably high probability of obtaining at least 35 with malignant masses.

Classification will be done using standard logistic regression models and ROC curves as appropriate. The sensitivity and specificity will be reported along with 95% two-sided confidence intervals, and an AUC relative to the ROC curve will be determined. It is assumed that 50 patients per year may enroll onto this study. Thus, an accrual period of 10 years is anticipated in order to enroll up to 500 subjects.

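### FNA feasibility, the first primary objective, has no planned estimate in Section 8, and no rule covers FNA samples that yield no usable marker result

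*Combined protocol and SAP*

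**What the plan says.** Section 1.1.1 of the combined protocol and SAP has two primary objectives. The first is "To evaluate the feasibility of molecular testing in adrenal neoplasm FNA biopsy samples". The second is "To determine the accuracy of novel diagnostic molecular markers in clinical adrenal FNA biopsy and surgically resected samples". The Précis repeats both.

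Section 8, the only statistical section, opens with one: "The primary objective of this study is to determine the ability of a set of markers to distinguish between benign and malignant adrenocortical neoplasms". Its method is "Classification will be done using standard logistic regression models and ROC curves as appropriate", and its reporting is "The sensitivity and specificity will be reported along with 95% two-sided confidence intervals", plus an AUC. On expected performance, "it is expected that the classification accuracy of the proposed methods will be 90% or better". It sets no feasibility endpoint, definition of an adequate sample, or criterion. It does not say what happens to a sample without a marker value, and it does not separate FNA from surgical samples.

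Other sections bear on how often an FNA may fail:
- Section 1.2 reports that for cytology "fine needle aspiration biopsy has a 67%-100% adequacy rate". It also cites adequate nucleic acid yield in thyroid FNA and detection from as few as 10 cells (Appendix B).
- Section 5.1.1 allows one biopsy. Pathology receives part of the sample and the molecular laboratory receives the rest.
- Sections 3.2 and 9.1 direct FNA to low-risk patients who do not need adrenalectomy. Patients who have adrenalectomy supply surgical tissue.

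**The concern.** There are two linked gaps.

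First, if Section 8 is followed as written, the study can finish without an estimate for its first primary objective. The material on thyroid samples and cell-line detection is rationale. It does not analyse this study's adrenal samples.

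Second, an FNA without usable nucleic acid cannot enter a logistic model or an ROC curve. With no rule for it, it leaves the analysis by default, and any FNA accuracy figure then describes adequate samples only. Section 1.2 says the markers would help most before surgery, in FNA samples. A patient whose FNA gives no result gets no answer from the test, so the adequate-sample figure alone does not show what an FNA patient can expect.

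**Working it through.** **Inputs from the documents.** Expected accuracy is 90%, used in Section 8 for both malignant and benign cases. Section 8 plans on 35 malignant and 200 benign cases. Cytologic FNA adequacy is 67%-100% (Section 1.2).

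**Assumptions.** The documents give no molecular adequacy for adrenal FNA, so the cytologic range stands in for it, with the same adequacy *a* in malignant and benign tumours. They also give no number of FNA attempts (200 assumed) and no number of malignant cases reached by FNA (9 of 35 assumed, about a quarter).

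**Step 1: the plan's own precision.** The half-width is 1.96 × √(p(1−p)/n) with p = 0.90.
- n = 35: 1.96 × √(0.09/35) = 0.099, the stated +/-9.9%.
- n = 200: 1.96 × √(0.09/200) = 0.042, the stated +/-4.2%.

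Both figures reproduce. They take every case to have a marker result.

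**Step 2: failures scored as not correctly classified.** Correct calls among all attempted FNAs = *a* × 0.90, for sensitivity and specificity alike.
- *a* = 0.67: 0.603
- *a* = 0.80: 0.72
- *a* = 0.90: 0.81
- *a* = 1.00: 0.90

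**Step 3: a no-result scored as malignancy not excluded.** Sensitivity = *a* × 0.90 + (1 − *a*), and specificity = *a* × 0.90.
- *a* = 0.67: sensitivity 0.603 + 0.33 = 0.933, specificity 0.603.
- *a* = 1.00: both 0.90.

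Under this convention sensitivity does not fall. Specificity carries the whole loss.

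**Step 4: where the effect lands.** If all 35 malignant cases came through FNA at 67% adequacy, 35 × 0.67 ≈ 23 would have a result, with half-width +/-12.1%. That is an upper bound. If a quarter came through FNA, 35 × 0.75 + 35 × 0.25 × 0.67 ≈ 32 would remain, with half-width +/-10.4%, close to the planned 9.9%. A pooled sensitivity is therefore little affected, while an FNA-specific one is imprecise: with 9 malignant FNA cases, 1.96 × √(0.09/9) = 0.196, about +/-20 points.

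**Step 5: can feasibility be estimated?** With 200 attempts and 80% adequacy, 1.96 × √(0.80 × 0.20/200) = 0.055, or +/-5.5 points. The study would hold enough data for a useful estimate.

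**The case against.** Section 8 never says that failed samples are excluded; that follows from its silence and the method it names. A reader might infer a decision to analyse complete cases only, but the documents do not state one. The supportable claim is that no rule exists and that the named method drops such samples by default. The specimen flow diagram in Section 5.1.1 is not shown, so an adequacy step in it cannot be checked.

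A reader might also infer that FNA accuracy is overstated by about 30 points. That needs adequacy at the bottom of a range quoted for cytology, and every failure scored as wrong. The range includes 100%, where the effect is zero. The thyroid yield and 10-cell detection do not establish adrenal molecular adequacy, but they count against taking 67% as the expected value. Step 3 shows that another reasonable convention removes the loss of sensitivity. Accuracy among adequate samples is also a legitimate quantity if the adequacy rate is reported beside it.

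Finally, most malignant cases should come from surgical tissue, and Section 8 promises no separate FNA accuracy figure, so there is no planned FNA headline to correct.

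These points stand and limit the claim about size. They do not supply the missing feasibility estimate or the missing rule.

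**Conclusion.** The point holds in this form. The first primary objective has no planned estimate, which needs no assumption beyond reading Sections 1.1.1 and 8 together. Section 8 also has no rule for FNA samples without a usable result, so FNA accuracy is conditional on an adequate sample by default.

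The size of the second gap is unknown. Under the assumed 67%-100% adequacy, with failures counted as not correctly classified, 90% becomes 60%-90% of attempted FNAs. With a no-result treated as malignancy not excluded, only specificity falls. Because FNA goes to low-risk patients, the effect bears mainly on FNA specificity. Surgical samples are outside it and pooled estimates are affected less. The documents do not support a claim that the study's overall sensitivity will be inflated by a known amount.

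**What to change.** In Section 8:

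1. List feasibility as co-primary. Define it as the proportion of all attempted FNAs that give a result sufficient for the prespecified classifier, with a 95% CI. A valid result on every listed marker should not be required: Appendix A reports an AUC of 0.907 for five genes combined against 0.913 for the best single gene, so a sample may be classifiable without the full panel. State beforehand what proportion would count as feasible.
2. Report FNA sensitivity and specificity separately from surgical samples, both among adequate samples and with all attempted FNAs in the denominator. State how a no-result is scored, and that FNA sensitivity is expected to be imprecise.

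The cost is Section 8 wording, one extra table and possibly one adequacy data field, since the case report form items in Section 6.1 do not name one. Section 5.2 already provides for sample tracking. The FNA accuracy figure may look less favourable. Enrolment and patient care do not change. Label: Cheap improvement.

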9 HUMAN SUBJECTS PROTECTIONS

9.1 RATIONALE FOR SUBJECT SELECTION

Subjects will be selected for this protocol based on a clinical diagnosis of an adrenal neoplasm. Only patients at low risk for a malignant tumor will undergo fine needle aspiration biopsy and those requiring an adrenalectomy will have surgical resected tissue to test the markers. Such a selection criteria for performing the fine needle aspiration biopsy would allow us to select those patients most likely to represent a diagnostic dilemma and to benefit from such an analysis.

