3 STUDY IMPLEMENTATION

This is a prospective study of individuals with an adrenal mass. Individuals will have routine clinical work up for an adrenal mass (see section 3.1); those with nonfunctioning tumors larger than 2 cm will undergo CT guided fine-needle aspiration biopsy. For patients who require adrenalectomy for a functioning tumor, the surgically resected tissue sample will be used for the molecular analysis.

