3.2 CT GUIDED FINE NEEDLE ASPIRATION BIOPSY OF ADRENAL NEOPLASM

- Patients with confirmed non-functional tumors greater than 2 cm in greatest dimension will undergo CT guided fine needle aspiration in the Interventional Radiology Department as per standard of care if they do not require an adrenalectomy.
- Tissue will be handled as described in Section [5.1.1](#)

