3.3 SURGICAL INTERVENTION

Patients with an adrenal neoplasm will have an adrenalectomy based on our standard clinical practice ([Appendix C*](#)).

*Patients with an adrenal mass measuring 2 – 4cm and suspicious imaging features for malignancy will be given the option of adrenalectomy.

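### Accuracy in FNA and in resected samples is a primary objective, but Section 8 plans no analysis by specimen type, and its 35-case precision covers all specimens together

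*Combined protocol and SAP*

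**What the plan says.** The second primary objective in Section 1.1.1 names both specimen types: "To determine the accuracy of novel diagnostic molecular markers in clinical adrenal FNA biopsy and surgically resected samples".

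Who supplies which specimen is set out in several places. Section 9.1 states "Only patients at low risk for a malignant tumor will undergo fine needle aspiration biopsy", with resected tissue used from patients who need surgery. Section 3.2 has confirmed nonfunctioning tumours over 2 cm biopsied "in the Interventional Radiology Department as per standard of care if they do not require an adrenalectomy". Section 3 is broader: "those with nonfunctioning tumors larger than 2 cm will undergo CT guided fine-needle aspiration biopsy", with no low-risk or no-surgery limit, while functioning tumours that need removal supply resected tissue. Section 3.3 adds that 2-4 cm masses with "suspicious imaging features for malignancy will be given the option of adrenalectomy".

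Section 5.1.1 places FNA material in RNAlater and snap-freezes resected tissue. It normalizes expression cutoffs to a carcinoma cell line and universal RNA, and the stated purpose is interassay variability.

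Section 8 restates the aim as one benign-versus-malignant question. Its targets are "Enrolling thirty five (35) patients who are ultimately determined to have malignant masses" (±9.9 points around 90%) and "Enrolling 200 patients who are ultimately determined to have benign masses" (±4.2 points). The planned output is "The sensitivity and specificity will be reported along with 95% two-sided confidence intervals", plus an AUC. Neither FNA nor resected tissue is mentioned.

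**The concern.** Under Sections 3.2 and 9.1, FNA samples come mainly from tumours thought unlikely to be malignant, and resected samples from tumours that need removal. If malignant cases are mostly frozen tissue and benign cases are more often FNA, any expression difference caused by sampling or preservation becomes mixed with the benign-malignant difference. A shift in one direction makes a marker look better than it is in either specimen; a shift in the other hides real discrimination. The normalization in Section 5.1.1 is not described as dealing with this.

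The stakes are highest for FNA, because Section 1.2 identifies preoperative use on FNA material as where the markers would help most. If Section 8 is followed as written, a single sensitivity could rest largely on resected tissue and be taken as FNA performance, with a precision that FNA alone may not have. The feasibility objective is not affected.

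**Working it through.** **1. Reproduce the plan's figures.** Inputs from Section 8: expected accuracy 90%, two-sided 95% interval. Half-width h = 1.96 × √(0.9 × 0.1 / m).
- m = 35 malignant: 1.96 × √(0.09/35) = 0.0994, or ±9.9 points.
- m = 200 benign: 1.96 × √(0.09/200) = 0.0416, or ±4.2 points.

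Both match, and 35 is the smallest count that meets the ±10 goal.

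**2. What the 35 counts.** Section 8 expects 10% malignancy among all enrolled patients: 0.10 × 350 = 35 and 0.10 × 500 = 50, whatever the specimen.

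**3. What FNA sensitivity would need.** To have ±9.9 points, about 35 malignant cases must have an evaluable FNA. That is 35/35 = 100% of those expected at N=350, or 35/50 = 70% at N=500. Section 1.2 gives 67-100% adequacy for cytology. If 67% applied to the molecular assay, an FNA in all 50 would yield 50 × 0.67 = 33.5 evaluable cases (±10.2). That is an assumption: the thyroid FNA experience in Section 1.2 and the 10-cell detection in Appendix B suggest molecular adequacy may be higher.

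**4. Low-risk scenarios.** The documents give neither the share of patients having FNA nor malignancy among them; both are assumed here. Malignant FNA cases = N × share × malignancy, at N=500 with full adequacy:

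| FNA share | 1% malignant | 5% malignant |
|---|---|---|
| 30% | 1.5 | 7.5 (±21.5) |
| 50% | 2.5 | 12.5 (±16.6) |
| 70% | 3.5 | 17.5 (±14.1) |

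Below about 10 cases the formula is not dependable. Exact (Clopper-Pearson) 95% intervals are 15.8-100% for 2 of 2 correct and 65.3-98.6% for 16 of 18, against 76.9-98.2% for 32 of 35.

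**5. A scenario under Section 3.** Its wording has no low-risk limit, so malignancy in the FNA group could exceed the overall 10%. With a 50% share and 14% malignancy, 500 × 0.50 × 0.14 = 35 cases, or ±9.9 points.

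**6. Specificity.** Benign FNA cases = N × share × (1 − malignancy). At N=500, full adequacy and 1-5% malignancy:
- 30% share: 142.5-148.5 cases (±4.9 to ±4.8)
- 50% share: 237.5-247.5 cases (±3.8 to ±3.7)
- 70% share: 332.5-346.5 cases (±3.2)

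So ±4.2 can hold for FNA specificity if about 200 evaluable benign FNAs are obtained.

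**The case against.** The best defence is that Section 8 never presents ±9.9 as FNA precision. It speaks of patients with malignant masses, and the figure is right for them. That stands: a reader might infer that the plan miscalculates or misattributes its precision, and it does neither.

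The objective can also be read jointly, with no promise of separate estimates. That is a possible reading, and pooling is implied by Section 8 rather than stated. But an objective that names two specimen types, obtained from patients at different risk, is not answered for FNA by one combined figure.

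The association between specimen and malignancy is only partial, because functioning tumours are also resected and suspicious 2-4 cm masses have only the option of surgery. A reader might infer that a pooled result must be inflated. The documents do not support that: neither the direction nor the size of any specimen effect is given.

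A reader might also infer from the low-risk scenarios that ±10 points is out of reach for FNA. Step 5 shows otherwise while the eligibility passages disagree.

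The specimen flow diagram in Section 5.1.1 and the Appendix C algorithm are not in the text available to me, so a specimen split shown there cannot be excluded. The point concerns Section 8. Finally, stratifying adds no malignant FNA cases; it only makes their number visible.

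**Conclusion.** The concern holds as a gap in the analysis plan that should be fixed. The primary objective covers two specimen types, the protocol's own rules make specimen likely to track malignancy, and Section 8 neither separates the two nor says how many malignant cases each will contribute. The FNA part of the objective could therefore go unanswered, or be answered by a confounded estimate.

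The firm figure is the requirement of about 35 evaluable malignant FNAs for ±9.9 points at 90% sensitivity. Having all or 70% of expected malignant cases in the FNA group is hard to square with restricting FNA to low-risk patients. The scenario counts are illustrations that depend on assumed FNA share and malignancy. The size of any pooling bias is unknown. Confidence is medium, given those unknowns and the missing diagram and algorithm.

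**What to change.** In Section 8:

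1. Report sensitivity, specificity and AUC separately for FNA and resected samples, with exact 95% intervals for the proportions. Treat FNA sensitivity and AUC as descriptive if malignant FNA cases are few.
2. Give any combined AUC only as a specimen-stratified estimate, and draw no FNA sensitivity claim from pooled data.
3. State that the 35-case, ±9.9-point precision is for all specimens together, and give the expected number of malignant FNA cases with the assumptions behind it.

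Separately, Sections 3, 3.2 and 9.1 differ on who receives FNA and must be reconciled; the expected count depends on the answer.

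The cost is wording and a stratified analysis of data already planned, with no new samples. The downside is that FNA sensitivity may become openly imprecise.

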9.2 PARTICIPATION OF CHILDREN

Because adrenal neoplasm are exceedingly rare in children and when present are more likely to be malignant, children will not be enrolled in this study.

9.3 PARTICIPATION OF SUBJECTS UNABLE TO GIVE CONSENT

Subjects who lose capacity to provide consent will be taken off study.

9.4 EVALUATION OF BENEFITS AND RISKS/DISCOMFORTS

Participants may experience no personal benefit from the study. There is however the potential benefits of increasing our ability to diagnose and predict the outcome of patients with malignant adrenocortical neoplasms. Each individual patient would have a complication risk of <1% associated with the fine needle aspiration biopsy.

9.4.1 Specimen Collection Risks

Risks also include those associated with specimen collection include pain, bleeding and the possibility of infection at the sampling site. Risk of biopsy: All care will be taken to minimize risks that may be incurred by tumor sampling. However, there are procedure-related risks (such as bleeding, infection and visceral injury) that will be explained fully during informed consent. If patients suffer any physical injury as a result of the biopsy, immediate medical treatment is available at the NIH's Clinical Center in Bethesda, Maryland. Although no compensation is available, any injury will be fully evaluated and treated in keeping with the benefits or care to which patients are entitled under applicable regulations.

